### Secondary Study Questions

- b. Is perioperative glucocorticoid administration more effective in improving range of motion for certain intra-operative elbow fractures or depending on the mechanism of injury (subgroup comparison based on fracture type and high-energy or low-energy injuries)?
- c. Do patients that receive perioperative glucocorticoids have a higher surgical site infection rate?

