### **Statistical Analysis**

- a. Primary analysis
  - i. Intention-to-treat
  - ii. Baseline characteristics between treatment arms will be compared using univariate descriptive statistics.
  - iii. Primary end-point (range of motion: continuous variable) → Univariate analysis of unmatched, interval variable with two groups assuming non-normal distribution: Mann-Whitney U Test will be performed.

- iv. Secondary end-points that are dichotomous (infection, revision surgery, heterotopic ossification, and other complication) will be analyzed with a chi-square or Fisher's exact test where the assumptions for a chi-square test are not met.
- v. Secondary end-points that are nominal or ordinal (Pain score, DASH score) will be analyzed using a Mann-Whitney U Test.

b. Subgroup analysis

- i. Analysis will be performed based on fracture type and stratification will make comparison possible.
- ii. Multivariate analysis using linear regression for the interval variable (range of motion) will be performed based on:
  1. Age <65 vs Age >65
  2. Mechanism of injury (High-energy vs. Low-energy)
  3. Treatment type
  4. Time from injury to surgery

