Statistical Analysis Plan (SAP)

Steroid Administration for Articular Fractures of the Elbow (SAFE Trial): A Randomized, Controlled Trial of Perioperative Glucocorticoids during Treatment of Intraarticular Elbow Fractures

Principal Investigator: [name]

Assistant Professor, Orthopaedic Surgery

Protocol Identification Number: 210125

Clinicaltrials.gov Identifier: NCT04738318

Version Date 03/09/2021

Statistical analysis plan

Demographics will be compared between each treatment arm in each stratification group for comparison and summary statistics for each treatment arm will be provided. If significant differences exist in patient, injury, or treatment variables, subgroup analysis will be performed. Assumptions for each variable will be assessed for normality using histograms and frequencies and cross tabulation will be tabulated for categorical and ordinal variables. If continuous data is not normally distributed, we will use non-parametric analysis methods. Graphical methods will be used to examine data distributions, identify influential observations, and perform transformations if needed. Prior to hypothesis testing, the data will be screened for errors and missing values using descriptive statistics and histograms. Suspicious values will be confirmed for accuracy and changes will be documented in an appendix. Every effort will be made to minimize missing or incomplete data. Study personnel will follow-up with all providers and patients to collect data. Data will be analyzed in a pragmatic fashion and all collected data will be analyzed.

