We will use the open-source statistical package R (R Development Core Team, 2012) and Stata 16 statistical software (StataCorp LLC, 2019, College Station, TX) for analysis. An intention-to-treat analysis will be conducted including all eligible patients as originally randomized. Analysis of each primary and secondary endpoint will be performed with all patients at each follow-up time point. Interactions for fracture-type and treatment group will be modeled at each follow-up time point and if significant, each fracture-type group will be independently analyzed. Multivariable proportional odds models for the Aim 1 dependent variable, range-of-motion, will be performed and multivariable logistic regressions will be performed for Aim 2 outcomes evaluating complications and safety. The Aim 3 dependent variable is continuous MME total and will be analyzed using a multivariable proportional odds model as the total amount consumed for each patient during the post-operative course.

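### Secondary question b asks whether the drug effect depends on injury energy, but no treatment-by-mechanism interaction is written; protocol and SAP also differ on when fracture types are analysed separately

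*SAP*

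**What the plan says.** Protocol section 2.0, Secondary Study Questions, item b, asks whether the drug is more effective in some groups than in others, and describes this as a "subgroup comparison based on fracture type and high-energy or low-energy injuries".

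Four places could supply the analysis:

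- **Protocol 10.0, Subgroup analysis, b.i** covers fracture type and sets no condition: "Analysis will be performed based on fracture type and stratification will make comparison possible".
- **Protocol 10.0, Subgroup analysis, b.ii** reads "Multivariate analysis using linear regression for the interval variable (range of motion) will be performed based on" and then lists four variables: age group, mechanism of injury (high against low energy), 'Treatment type', and time from injury to surgery. No product term appears.
- **SAP, analysis paragraph** specifies one interaction, fracture type by treatment: "Interactions for fracture-type and treatment group will be modeled at each follow-up time point and if significant, each fracture-type group will be independently analyzed". The SAP does not mention mechanism or injury energy.
- **SAP, opening paragraph** has another subgroup trigger: "If significant differences exist in patient, injury, or treatment variables, subgroup analysis will be performed". It follows the comparison of demographics between arms.

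The model also differs. The protocol uses linear regression for range of motion; the SAP says "Multivariable proportional odds models for the Aim 1 dependent variable, range-of-motion, will be performed". The Enrollment Goal (section 5.0) and Sample Size Justification (section 10.0) set 18 patients per arm within each fracture type, 144 in all. The protocol's primary test reads as a single two-group comparison: "Univariate analysis of unmatched, interval variable with two groups assuming non-normal distribution: Mann-Whitney U Test will be performed".

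**The concern.** Whether a drug works better in one group than in another is a question about effect modification. It needs a contrast of treatment effects between the groups. A main effect of mechanism shows only whether high-energy elbows end up stiffer on average. A subgroup trigger based on differences in patient or injury variables does not test effect modification either.

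For injury energy, then, the model that answers a declared secondary question would be chosen after the data are seen. An additive model, separate tests in each group and an interaction model all fit the present wording, and only the last tests question b directly.

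For fracture type a test is specified, but the documents disagree on whether separate stratum analyses follow always or only after a significant interaction. That matters because the trial is sized by stratum.

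**Working it through.** **1. The plan's own figure.** Inputs from Sample Size Justification: difference 25 degrees, SD 17, alpha 0.05 (two-sided assumed), power 90%. The noncentral t calculation gives power 0.875 with 10 per arm and 0.906 with 11, so 11 per arm (22 per fracture type) reproduces. No power calculation is given for any interaction.

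**2. Evaluable numbers.** The 20% allowance combines loss of about 10% with taper non-compliance, and the Noncompliance paragraph (section 6.0) keeps non-compliers in their randomised arm. The range is therefore 144 × 0.8 = 115 to 144 × 0.9 = 130. Per arm per stratum it is 18 × 0.8 = 14 to 18 × 0.9 = 16.

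**3. Treatment-by-mechanism term, mechanism unrelated to fracture type.** With high-energy share q (assumed; the documents give none) and 1:1 allocation:

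SE = 17 × √(4/(Nq) + 4/(N(1−q))), df = N − 4.

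| N | q | SE | 95% CI half-width | Power for 15 degrees |
|---|---|---|---|---|
| 115 | 0.2 | 7.93 | 15.7 | 0.47 |
| 115 | 0.3 | 6.92 | 13.7 | 0.58 |
| 115 | 0.5 | 6.34 | 12.6 | 0.65 |
| 130 | 0.2 | 7.45 | 14.8 | 0.51 |
| 130 | 0.3 | 6.51 | 12.9 | 0.63 |
| 130 | 0.5 | 5.96 | 11.8 | 0.70 |

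The 15 degrees is also assumed (for example, an effect of 25 in one group and 10 in the other). Simulated proportional odds models (arc rounded to 5 degrees and capped at 150, likelihood ratio test, 2,500 trials) gave similar power for q of 0.3 to 0.5: 57-64% at 115 and 62-68% at 130.

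**4. The same term when mechanism is related to fracture type.** Beside a treatment-by-fracture-type interaction with equal strata, SE = 17 × √(4/(N × mean of q(1−q) over strata)), df = N − 10.

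| Assumed shares by stratum | Mean q(1−q) | N | SE | CI half-width | Power |
|---|---|---|---|---|---|
| 10/20/30/60% | 0.175 | 115 | 7.58 | 15.0 | 0.50 |
| 10/20/30/60% | 0.175 | 130 | 7.13 | 14.1 | 0.55 |
| 10/30/70/90% | 0.150 | 115 | 8.19 | 16.2 | 0.44 |
| 10/30/70/90% | 0.150 | 130 | 7.70 | 15.2 | 0.49 |

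**5. The SAP's fracture-type condition.** With stratum effects e and n per arm per stratum, the F test has 3 and 8(n−1) df and noncentrality Σ(e − mean)²/(2 × 17²/n). The SAP gives no level; 0.05 is assumed.

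| Effects across strata (assumed) | n = 14 | n = 16 |
|---|---|---|
| 25/0/0/0 | 0.80 | 0.86 |
| 25/25/0/0 | 0.91 | 0.95 |
| 25/15/10/5 | 0.45 | 0.51 |
| 25/10/10/10 | 0.35 | 0.40 |
| 25/12.5/12.5/12.5 | 0.25 | 0.29 |

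With a uniform effect the condition is met about 5% of the time per test. The 95% CI half-width for the effect within one stratum is t × 17 × √(2/n): 13.2 degrees at n = 14 and 12.3 at n = 16.

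**6. Multiplicity of full reporting.** Four fracture types plus two mechanism groups give six estimates per arc per visit. With no true effect, simulation (3,000 trials, arc correlation 0 or 0.5) puts the chance of at least one p < 0.05 at one visit at 24-26% for one arc and 40-44% for both. As a check, independence would give 1 − 0.95⁶ = 26% and 1 − 0.95¹² = 46%. Four visits and two arcs would make 6 × 2 × 4 = 48 estimates, with a higher chance.

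**The case against.** The protocol's regression list stands under the heading Subgroup analysis, and question b is itself called a subgroup comparison. A fair reader could take this as a planned, loosely specified mechanism subgroup analysis, with an interaction intended. That stands as a reading of intent. It does not supply the term, and the SAP shows that an interaction is written out when one is wanted.

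Testing the interaction before analysing strata separately is conventional, and that stands too. A reader might go further and infer that the SAP withholds stratum estimates when the interaction is not significant. The text does not say so. It makes independent analysis conditional, a fitted interaction model already contains stratum effects, and the protocol plans the fracture-type analysis unconditionally. What remains is a conflict between the documents.

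A reader might also infer that the mechanism coefficient is meant to answer question b. Neither document proposes that.

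Finally, power for the new term is modest. This is a reason to label the result exploratory and report an interval. It is not a reason to leave the analysis unspecified.

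**Conclusion.** The point holds. The injury-energy half of question b has no treatment-by-mechanism interaction in either document, and the analysis as written does not measure effect modification by mechanism. The fracture-type half has a valid interaction test, but the protocol and SAP disagree on whether separate stratum analysis depends on it.

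Once specified, the mechanism contrast would have a 95% CI of about ±12 to 16 degrees, against the 25-degree design effect. Power for a 15-degree difference would be about 47-70% if mechanism is unrelated to fracture type, and about 44-55% under the related patterns shown. These figures rest on the plan's SD of 17 and on assumed high-energy shares and effect patterns.

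It would be wrong to conclude that the trial's main result is at risk: the pooled primary comparison is unaffected and still answers a uniform effect. The change should be made, at the lower end of that priority, as a cheap improvement.

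**What to change.** 1. Add a treatment-by-mechanism product term to the range-of-motion model in the SAP and in protocol 10.0 b.ii, for both arcs. Name one visit (for example 6 months) as the main one for question b. Define high and low energy, and say whether 'Treatment type' means the randomised arm.
2. Keep the interaction tests, but do not let their p-values decide what is reported. Possible wording: *Treatment effects with 95% confidence intervals will be reported for every fracture type and both mechanism groups whatever the interaction p-value; they are exploratory and unadjusted for multiplicity.* State the effect scale, degrees or odds ratio.
3. Reconcile protocol 10.0 b.i (unconditional) and b.ii (linear regression) with the SAP (conditional, proportional odds).

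**Cost.** A few sentences in each document, one model term and a forest plot. Injury information is already recorded at the Enrollment Visit (section 6.0), so no extra patients or visits are needed. The downsides are the wide interval for mechanism and the multiplicity shown above; the exploratory label and the single named visit address the second.

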### **Enrollment Goal**

We will seek to enroll 18 patients in each treatment arm per fracture type and 18 patients in each control arm, for a total of 144 patients.

Fracture Type	Treatment Arm	Control Arm	Total
Distal humerus fracture	18	18	36
Radial head	18	18	36
Proximal ulna	18	18	36
Combined	18	18	36
			144

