## **10.0 Statistical Considerations**

### **Sample Size Justification**

Prior studies suggest Flexion/extension arc after intra-articular fracture  $\sim 105^\circ$ . Difference suggested by prior retrospective study with dexamethasone shows potential improvement ( $\delta$ ) of  $27^\circ$  (avg post-operative AROM  $132.5^\circ$ ). Conservatively, will attempt to see an improvement of  $25^\circ$  ( $\delta$ ). Average standard deviation from literature of post-operative intra-articular elbow fractures range of motion is  $17^\circ$  ( $\sigma$ ). A total of 22 patients are needed (11 treatment and 11 control) to be able to reject the null hypothesis with 90% power and  $\alpha = 0.05$ . Assuming a 20% loss to follow-up based on prior studies ( $\sim 10\%$ ) + non-compliance of six-day home taper course. As we are stratifying our treatment and control groups based on fracture type, we will need 18 patients in each treatment arm for each fracture and 18 patients in each control arm.

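### For surgical site infection, the protocol and SAP name different analyses without ranking them; the SAP's logistic model can fail if infections are rare, and neither specifies a risk difference with an interval.

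*SAP*

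**What the plan says.** The second of the protocol's two secondary questions (Section 2.0, item c) is "Do patients that receive perioperative glucocorticoids have a higher surgical site infection rate". Section 10.0, Statistical Analysis, item a.iv, lists the dichotomous endpoints as "infection, revision surgery, heterotopic ossification, and other complication" and says that they "will be analyzed with a chi-square or Fisher's exact test where the assumptions for a chi-square test are not met".

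For the same family of outcomes the SAP says that "multivariable logistic regressions will be performed for Aim 2 outcomes evaluating complications and safety". It names no covariates for these models and no method for sparse events. It also plans to analyse every endpoint at every follow-up visit, to model the interaction of fracture type with treatment at each visit, and to analyse each fracture type separately if that interaction is significant. The protocol letters its questions a to c, so the SAP's Aim 2 has no definition there.

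The sample size section concerns range of motion only. The documents give no power, precision or margin for infection, and no numerical infection rate.

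**The concern.** The question about infection has two candidate analyses and no stated order between them, so the choice could be made after the data are seen.

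Each also has a weakness when infections are few. Maximum-likelihood logistic regression has no finite treatment odds ratio when one arm has no infections, and an interaction model fails more easily because it needs events in every arm-by-fracture cell. The chi-square or Fisher test always gives a p-value, but a p-value does not say how large an excess of infection remains compatible with the data. With few events, a non-significant result is likely even if the infection rate doubles, and nothing in the plan guards against treating it as reassurance.

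**Working it through.** **Inputs from the documents.** Enrolment: "18 patients in each control arm, for a total of 144 patients", so 72 per arm overall and 18 per arm in each of four fracture types. Attrition: "Assuming a 20% loss to follow-up based on prior studies". 144 × 0.8 = 115.2, or about 58 per arm. Alpha is 0.05, taken as two-sided.

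**Assumption.** The infection rate is taken as 2% to 10%, because the documents give none.

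**The plan's own figure.** The protocol states: "A total of 22 patients are needed (11 treatment and 11 control". With a difference of 25° and SD 17°, the normal approximation is n = 2 × (1.960 + 1.282)² × (17/25)² = 9.7, so 10 per arm. The exact two-sided t calculation gives power 0.875 at 10 and 0.906 at 11. The figure of 11 is confirmed, but it says nothing about infection.

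**1. Pooled logistic model.** With the same rate p in both arms, the chance that at least one of two arms of size n has no infections is 1 − [1 − (1 − p)^n]². For p = 2% and n = 72: 0.98^72 = 0.2335, and 1 − 0.7665² = 0.41.

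| Assumed rate | Expected infections in 144 | No finite treatment OR, 72 per arm | 58 per arm |
|---|---|---|---|
| 2% | 2.9 | 41% | 52% |
| 3% | 4.3 | 21% | 31% |
| 5% | 7.2 | 5% | 10% |
| 10% | 14.4 | 0.1% | 0.4% |

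**2. Interaction model.** There are 8 arm-by-fracture cells of 18. The chance that at least one is empty, which makes at least one coefficient infinite, is 1 − [1 − (1 − p)^18]^8. At 5%, 0.95^18 = 0.397 and the result is 98%. At 10%, 0.90^18 = 0.150 and the result is 73%. At 2% it exceeds 99%.

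**3. Separate analysis of one fracture type (18 per arm).** The formula of step 1 gives a zero-event arm in 91%, 64% and 28% of trials at 2%, 5% and 10%.

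**4. Power of the unadjusted test.** Fisher's exact test, by full enumeration:

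| Comparison | 58 per arm | 72 per arm |
|---|---|---|
| 2% vs 4% | 1% | 2% |
| 5% vs 10% | 8% | 12% |
| 10% vs 20% | 24% | 32% |

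Where expected counts allow chi-square, the normal approximation at 72 per arm gives about 20% for 5% vs 10% and 39% for 10% vs 20%, still far below the 90% planned for range of motion.

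**5. What a risk difference would show.** For 3 of 72 in each arm, each proportion is 4.17% with Wilson limits 1.43% and 11.55%. The Newcombe half-width is √[(4.17 − 1.43)² + (11.55 − 4.17)²] = 7.9 points.

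| Infections, treated vs control | Per arm | Difference (95% CI), points | Fisher p |
|---|---|---|---|
| 3 vs 3 | 72 | 0.0 (−7.9 to 7.9) | 1.0 |
| 3 vs 3 | 58 | 0.0 (−9.6 to 9.6) | 1.0 |
| 4 vs 2 | 72 | 2.8 (−4.8 to 10.9) | 0.68 |
| 3 vs 0 | 72 | 4.2 (−1.6 to 11.5) | 0.245 |

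In the last row the odds ratio is not finite, but the risk difference and its interval exist.

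**6. Common complications.** Section 1.0 of the protocol gives complications above 50%, re-operation up to 30%, heterotopic ossification limiting motion in up to 40%, and contracture release in 12-20%. The formula of step 1 with 72 per arm gives 0.02% at 12% and effectively zero from 20% upward.

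**The case against.** **The two analyses may be complementary.** Protocol Section 10.0 already pairs univariate tests with a multivariable regression, and the SAP's logistic models could be the adjusted tier for dichotomous outcomes. A failed model would then leave the unadjusted test standing. This is a fair reading, and it is why the point is an unreconciled difference and not a contradiction. Neither document says so, however.

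**The model usually gives an interval.** Logistic regression normally yields an odds ratio with a confidence interval, and the SAP promises summary statistics by arm. That stands. What is missing is an absolute difference, any stated interval, and an interval that survives a zero-event arm.

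**The failure rate can be overstated.** A reader might infer that the logistic model would nearly always break down. In simulations of 116 patients with eight parameters, some coefficient was infinite in 97%, 91%, 73% and 17% of data sets at 2%, 3%, 5% and 10%. That count includes coefficients other than treatment, such as a fracture type with no events, which leaves the treatment odds ratio finite. The treatment coefficient alone was infinite in about 53%, 36%, 8% and 0%, close to the table in step 1. The eight-parameter model also borrows covariates that the protocol lists only for range of motion.

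**Other complications.** A reader might extend the problem to every complication. The protocol's own rates rule this out for the pooled models.

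**Denominator.** The 20% allowance appears to combine about 10% loss with non-compliance, and non-compliers stay in an intention-to-treat analysis. Fifty-eight per arm is therefore probably pessimistic; the range from 58 to 72 covers this.

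**Misreading of p>0.05.** The documents nowhere say that non-significance will be called safety. The point is that the plan offers nothing better to report.

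**Conclusion.** The concern holds for infection and other rare events. The documents leave two unranked analyses and specify no absolute difference with an interval for the infection question.

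How often the logistic model fails depends on an infection rate that the documents do not supply. In the pooled model, loss of the treatment odds ratio is a substantial risk at about 3% or lower, uncommon at 5% and negligible at 10%. In the SAP's interaction model, at least one coefficient is lost in most trials across the whole assumed range. Analysing each visit's new infections separately would thin the events further. The low power for a doubling also holds across the range.

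These figures assume equal rates in both arms for steps 1 to 3, equal rates across fracture types, and a two-sided 5% level. The documents do not support a claim that the pooled models for heterotopic ossification, re-operation or overall complications are at risk.

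**What to change.** In the SAP:

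- Name the protocol's test, chi-square with Fisher's exact test when expected counts are small, as the main unadjusted analysis of the dichotomous endpoints, and state the expected-count rule.
- For infection, count participants with an infection over the whole follow-up, report the risk difference with a Newcombe 95% confidence interval, and answer question c from that interval. State that p>0.05 will not be described as absence of excess infection.
- If a model is kept for infection or other rare events, use Firth-penalised logistic regression with arm and fracture type only, and no interaction or by-fracture-type model.
- Keep ordinary logistic regression for the common complications, and name its covariates.
- Define Aim 2 by listing its endpoints.

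The cost is a change of SAP wording, with no effect on sample size or data collection. The downside is fewer covariates and no fracture-type interaction in the infection model.
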